Participants in this arm will attend an orientation session via Zoom that will last 60-90 minutes. They will connect with a research associate 3 times per week for 3 weeks after quit date via zoom where they will answer a few questions about their quitting progress, report on past 7-day smoking, and provide a sample of CO to verify their smoking status after their quit date using a portable CO monitor (coVita iCO™ Smokerlyzers®) and/or NicoTests saliva screen test that has been mailed to them. Those who proved their abstinence (CO< 8 ppm using coVita iCO™ Smokerlyzers®) and/or 30 ng/mL using NicAlert) [14] will receive a cash reward. The first successful CO sample earns \$5 cash, and then the reward increases by \$2 for each consecutive successful CO and/or saliva sample (e.g., \$5, \$7, \$9...). Participants also earn \$2 bonus for 4 consecutive successful CO and/or saliva samples (total=\$4). In all, participants can earn a maximum of \$176. Participant who fail the CO and/or saliva test will not receive reinforcement and the value of the next payment will be reset to the one that was missed.

Figure (1): overview of the study design

All participants will be asked to complete an end of treatment assessment 2 weeks after the intervention ends, which will be the same as the 3-month follow-up described below. Breath CO and/or saliva sample test (for cotinine analysis) will be collected at the end of treatment assessment via Zoom for participants who report they have quit.

All participants will be asked to complete a follow-up assessment 3 months after their quit date to assess their smoking status as well as get information about concomitant smoking and NRT use, use of additional NRT or cessation drugs (e.g., bupropion), and use of other tobacco methods. Breath CO and/or saliva sample test (for cotinine analysis) will be collected at the 3-month follow-up points for participants who report abstinence. The breath sample will be collected with the portable CO monitor (coVita iCO™ Smokerlyzers®) and/or NicoTests saliva screening test. A cut-off of 8 ppm for CO test (using coVita iCO™ Smokerlyzers®) and/or ≤ 30 ng/mL for the saliva sample test (using NicoTests) will be used to determine abstinence (Benowitz et al 2002).

Study measures

1. Baseline Assessment: All study materials and instrument will be translated into Spanish.

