- All baseline assessment will be re-administered except demographics.

- Information on number of sessions that was attended.
- *Acceptability:* The acceptability will be assessed by 3 items “How satisfied were you with the intervention?”, “How likely are you to recommend this intervention to a friend?” and “How useful was the intervention?”
- *Smoking Cessation:* Main smoking cessation outcome is 7-day point-prevalence abstinence (defined as self-report of not smoking in the past 7-days; not even a puff) and confirmed smoking cessation by expired carbon monoxide (CO) level cutoff of < 8 ppm using a coVita iCO™ Smokerlyzer® and/or NicoTests saliva sample of ≤ 30 ng/mL at the 3-month follow up. Secondary outcomes include the reduction in number of cigarettes smoked per day.[23,24] Relapse is defined as smoking at least once/week on two consecutive weeks.[25] These are described in more detail below.
- *Process evaluation:* Semi-structured post-intervention evaluation interviews will be conducted with randomly selected participants to further inform our assessment of acceptability and perceived helpfulness of interventions, and identifying key areas for refining the intervention protocols (e.g., improving access, content, usability). These will be conducted in-person or via Zoom and participants will receive \$25 for completing the interview.

Primary Outcome Measure Title: Smoking cessation - 7-day point-prevalence abstinence.

Outcome Measure Description:

Defined as self-report of not smoking in the past 7-days, not even a puff and confirmed by expired carbon monoxide (CO) level cutoff of < 8 ppm using a coVita iCO™ Smokerlyzer® and/or NicoTests saliva sample of ≤ 30 ng/mL.

Outcome Measure Timeframe:

4 weeks (end of treatment), and 3 months

Secondary Outcomes

1. Treatment-specific retention rates for study measures.
 - Defined as: Percentage of participants completing all study procedures divided by total enrolled. Coded reasons for dropouts.
 - Timeframe: 3 months
2. Treatment-specific adherence rates to study protocol
 - Defined as number of phone-call check-ins attended by each participant (4 for mindfulness training, 12 for contingency management).
 - Timeframe: 3 months

6) Data and Specimen Banking*

There will be no data or specimen banking.

7) Data Management*

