The analysis of the feasibility and acceptability outcomes will be mainly descriptive. We will calculate differences in pre and post intervention measures of baseline characteristics, indices of treatment implementation, adherence, retention, and treatment perceptions and compare the differences between arms 1 and 2. Attrition analyses will compare respondents who complete all measurements to those who do not based on baseline characteristics. Direct maximum likelihood estimation and multiple imputation will be used to address incomplete data. Univariate and multivariable logistic regression models will be used to explore baseline predictors of 3-month smoking cessation and the acceptability and feasibility of the intervention. Cross-tabulations for ordinal variables and mean and corresponding 95% confidence intervals for continuous variables will be used to explore secondary outcomes including improvement in depression, smoking self-efficacy, craving, quality of life, and mindfulness skills. Although we are unpowered to detect differences by gender, we will consider exploring the gender effect on our main outcomes in our analysis. Data management for preparing data for statistical analysis and statistical analysis will be performed with SAS or R statistical software.

Qualitative analyses of semi-structured post-intervention evaluation interviews will identify emergent themes related to acceptability and specific targets for refinement of content and delivery. Interviews will be audio-recorded, transcribed verbatim, and analyzed using Nvivo. This program is designed for the storage, coding, retrieval, and analysis of qualitative data. Two complementary coding schemes will be used: 1) descriptive, which uses words or short phrases to summarize passages of data and 2) in Nvivo, in which actual language from participants is used to name concepts and themes. Extensive analytic memos will be written after each interview is conducted, coded, and throughout the analysis process to reflect on code choices, emergent themes and patterns, and conceptual models. Finally, the data will be themed, in which the final sets of codes and their meanings will be transformed into longer and more descriptive themes to organize recurrent meanings and patterns. Themes and definitions will be compared across interviews to ensure consistency and reliability.

Statistical analyses will be done using SPSS, V21, (<https://www.ibm.com/analytics/spss-statistics-software>).

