Our team of multi-disciplinary experts in smoking cessation, MT, and analysis is a pioneer in developing and testing novel smoking cessation interventions among high-risk populations. Drs. [name] and [name] have long-term collaboration on several epidemiological studies and community-based cessation trials.[26-28] [name] (PI) is a Research Assistant Professor in the Department of Public Health Sciences at the University of Miami (UM). She has more than 10 years of experience in tobacco research. She had led several clinical- and community-based smoking cessation trials.[29-32] [name] (Co-I) has been involved in tobacco research for over 20 years. Recently, he has been evaluating mindfulness-based interventions

targeting high-stress occupational groups, and he will assist [name] in the development and testing of the proposed intervention.

14) Prior Approvals

N/A

15) Recruitment Methods

Our target sample size is up to 100 HIV patients who smoke (50 in each arm). Flyers will also be distributed at UM/HIV clinics and various community-based clinics/organizations not directly affiliated with UM/HIV, such as Jackson Health System (JHS). We will also recruit via advertisements on social media platforms.

Those interested will contact our research team to first determine eligibility or they may scan the QR code included on the study flyer to complete the screening questions independently via REDCap. Those completing the screening questions independently via REDCap will be assigned a subject ID and will then be directed to a separate form asking for their name and contact information, in case needed to be reached. If eligible, the research staff will provide an overview of the research study, and if the participant wants to participate, we will send them a link to complete the electronic informed consent and baseline survey via REDCap.

We are requesting permission to collaborate with another study, Project CHARM (IRB#20160911), which serves as a consent to contact database, to contact eligible participants. They will provide us with contact information for participants in their study who might be eligible for our study and have consented to be contacted by other studies.

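### Comparing pre-post differences between arms on the continuous scales will usually be less precise than adjusting follow-up scores for baseline, and the plan names no baseline-adjusted model

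*Combined protocol and SAP*

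**What the plan says.** Section 7 (Data Management) holds the analysis plan. One sentence begins "We will calculate differences in pre and post intervention measures of baseline characteristics", continues with treatment implementation, adherence, retention and treatment perceptions, and ends with the intention to "compare the differences between arms 1 and 2". A later sentence in the same section turns to "secondary outcomes including improvement in depression, smoking self-efficacy, craving, quality of life, and mindfulness skills" and plans to summarise them by "mean and corresponding 95% confidence intervals for continuous variables". That later sentence does not itself name a comparison between arms.

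No baseline-adjusted model is named for any scale. The only regressions specified are logistic, for predictors of 3-month cessation and of acceptability and feasibility. Direct maximum likelihood and multiple imputation are named for incomplete data, without a model or covariates.

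The baseline scores needed for adjustment will exist. Section 5 (Study measures) lists the scales at baseline and says of the 3-month visit: "All baseline assessment will be re-administered except demographics". Section 5 also describes the end-of-treatment assessment as one "which will be the same as the 3-month follow-up described below", which puts the scales there too, although the itemised list for that visit does not repeat them. Section 15 (Recruitment Methods) sets the target at up to 100 participants, 50 per arm.

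**The concern.** The natural reading of pre and post measures of baseline characteristics is the set of scales given at baseline and repeated later. On that reading, the between-arm estimate for each scale is a difference in mean change.

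A change score subtracts the whole baseline value, whatever its correlation with the follow-up value. When the two are only moderately correlated, that subtracts too much and adds baseline noise to the contrast. A model with baseline as a covariate subtracts only the part that predicts follow-up. At stake is the width of the intervals on the exploratory scales. In a pilot with no stated power or effect size, those intervals are most of what the scale analysis can offer.

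**Working it through.** The plan gives no power, SD, correlation or sample-size calculation, so there is no figure of its own to reproduce.

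**Inputs**
- n = 50 per arm (Section 15).
- 95% intervals (Section 7).
- ρ, the baseline to follow-up correlation: not in the documents; assumed 0.3 to 0.9.
- k, follow-up SD divided by baseline SD: not in the documents; 1 in the main case, 0.8 to 1.5 as sensitivity. The baseline SD is set to 1.
- Participants are treated as independent. Mindfulness training is delivered in groups, so this is a simplification.

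**Formulas for the variance of the arm difference, k = 1**
- Change score: (2/n) × 2(1 − ρ)
- Baseline-adjusted: (2/n) × (1 − ρ²) × [1 + 1/(2n − 4)]. The bracket is the cost of estimating the slope; at n = 50 it is 1 + 1/96, about 1%.

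**Example, ρ = 0.5.** Change score: 0.04 × 1.0 = 0.0400, SE 0.200. Adjusted: 0.04 × 0.75 × 1.0104 = 0.0303, SE 0.174. Variance ratio 0.0400/0.0303 = 1.32; interval ratio √1.32 = 1.15.

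| ρ | SE, change | SE, adjusted | Variance ratio | Change-score CI wider by |
|---|---|---|---|---|
| 0.3 | 0.237 | 0.192 | 1.52 | 23% |
| 0.5 | 0.200 | 0.174 | 1.32 | 15% |
| 0.7 | 0.155 | 0.144 | 1.16 | 8% |
| 0.9 | 0.089 | 0.088 | 1.04 | 2% |

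A simulation of 20,000 trials at 50 per arm gave variance ratios of 1.51, 1.33, 1.17 and 1.04. With 40 or 25 per arm and ρ = 0.5 the ratio is 1.32 or 1.31, so dropout hardly changes it.

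**In terms of sample size.** In large samples the adjusted analysis needs (1 + ρ)/2 as many participants. At ρ = 0.5 that is 50 × 0.75 = 37.5, so about 38 per arm match 50 per arm analysed by change scores. The difference detectable with 80% power at two-sided 5% is 0.56 SD for change scores and 0.49 SD with adjustment. At ρ = 0.3 these are 0.66 and 0.54 SD; at ρ = 0.7, 0.43 and 0.40 SD.

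**When the loss disappears.** For general k the large-sample variance ratio is (k² + 1 − 2ρk) / [k²(1 − ρ²)]. Numerator minus denominator is (1 − ρk)², so the ratio is 1 only when ρk = 1.
- k = 1.25, ρ = 0.8: 1.00
- k = 1.5, ρ = 0.7: 1.002
- k = 0.8, ρ = 0.5: 1.75

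At k = 1 and 50 per arm, the 1% slope cost makes the methods tie at ρ of about 0.98; at ρ = 0.99 change scores are marginally better (ratio 0.995).

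**Baseline imbalance.** The arm difference in baseline means has SD √(2/50) = 0.20. An imbalance of that size shifts the change-score contrast by (1 − ρ) × 0.20 in magnitude, or 0.10 SD at ρ = 0.5. Its contribution to the variance is (1 − ρ)² × (2/n) = 0.25 × 0.04 = 0.010. That is exactly the gap between 0.040 and 0.030, the change-score and adjusted variances before the slope cost.

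**The case against.** **The text does not say that the scales will be compared by change score.** The sentence with the arm comparison follows a statement that the feasibility and acceptability analysis is mainly descriptive, and its list includes items with no baseline value. The sentence on the scales has no arm contrast. This stands in part: the change-score reading is reasonable but not explicit. On either reading, though, no baseline-adjusted estimate is planned.

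**The outcomes are exploratory.** This limits the importance of the point but does not remove the loss. The plan commits to comparing arms and to 95% intervals, and the Background gives potential efficacy as an aim.

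**Direct maximum likelihood may already use baseline.** A likelihood model with baseline as a repeated measure could do so. The plan specifies no such model, so adjustment is neither stated nor excluded.

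**Stronger readings that the documents do not support.** A reader might infer that every scale estimate loses precision. That cannot be shown, because neither ρ nor the SDs are given and the loss is nil near ρk = 1. A reader might also count carry-over of baseline imbalance as a bias on top of the wider intervals. Randomisation keeps the contrast unbiased, and the carry-over is the extra variance itself. Finally, a reader might suppose that these estimates will feed a full trial. The word pilot suggests it, but the documents do not say so.

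**Conclusion.** The point holds as a modest, low-cost improvement in precision. If the Section 7 comparison covers the scales, change-score intervals would be about 23% to 8% wider than baseline-adjusted ones for ρ from 0.3 to 0.7. This assumes equal SDs, independent participants and 50 per arm. The loss is only 2% at ρ = 0.9 and zero where ρk = 1.

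It is confined to the exploratory continuous scales. The primary outcome is binary abstinence and is untouched, as are the listed secondary outcomes of retention and adherence. Adherence, retention and treatment perceptions also appear in the quoted sentence, but they have no baseline value to adjust for. It would be wrong to conclude that the planned contrast is invalid or that a primary conclusion is at risk.

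**What to change.** In Section 7, state that for each continuous scale, at each stated time point, the between-arm difference will come from a linear model of the follow-up score on stage 1 randomised arm plus the participant's own baseline score. Report the adjusted difference with its 95% CI. Keep raw pre-post change as within-arm description.

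Two details need stating:
- **Arm at 3 months.** Non-responders are re-randomised at stage 2 to switch or continue (Section 5). Say that the 3-month contrast is by stage 1 arm and averages over stage 2 assignment.
- **Cigarettes per day.** Section 5 lists its reduction as a secondary outcome. Adjust for baseline here too, but use a method suited to a skewed count with many zeros, as is likely after a quit attempt, instead of a plain linear model.

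The cost is a few sentences of wording, one degree of freedom per model (about 1% of variance at 50 per arm) and slightly more analysis work. No new data are needed.

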Protocol Title

A Pilot SMART Testing an Integrative Smoking Cessation Intervention for HIV Patients

Protocol Number:

20201296

Protocol Version

12

Protocol Version Date

10/6/23

Principal Investigator

[name], MSPH, MD

NCT Number

NCT05030766

1) Objectives*

We will conduct a pilot Sequential, Multiple Assignment randomized clinical trial (SMART) incorporating nicotine replacement treatment (NRT), contingency management (CM), and mindfulness training (MT) to identify the optimal dynamic strategy to promote biomarker-confirmed smoking abstinence among people living with HIV (PLWH).

2) Background*

Mindfulness training (MT) is an approach that has become more widely used for the purposes of smoking cessation. MT can operationalized into two components: 1) maintaining attention on immediate experience, and 2) maintaining an attitude of acceptance toward that experience, which can improve individuals' ability to avoid absorption in maladaptive mental patterns, behaviors, and emotional reactions that lead to depression.[1,2] [ENREF 40](#) MT is effective in reducing both self-report and objective indices of negative affect and psychological stress.[3,4] MT also can help smokers control craving by being less emotionally reactive and less prone to relapse related to avoidance of distressing symptoms.[5] The use of MT for smoking cessation, however, has not been tested among Hispanics HIV patients who smoke. We, therefore, propose to test the feasibility, acceptability, and potential efficacy of a mindfulness smoking cessation intervention among Hispanics HIV patients that smoke. CM is an evidence-based behavioral intervention where individuals receive escalating tangible reinforcement for biologically confirmed substance abstinence.[6] CM has been successful in retaining patients in treatment and fostering stable periods of abstinence in substance use behavioral research, including tobacco.[7-9] In HIV patients, CM was feasible and effective in improving compliance to ART[10] and reducing HIV risk behaviors (e.g., unprotected sex, injection drug use).[11] CM may as well reduce the economic stressor for smoking cessation (e.g., unemployment) in HIV patients. [12,13] Yet, no studies to date tested CM to promote smoking cessation among HIV smokers. In our survey among HIV smokers, 45.7% were interested in CM to quit smoking. Therefore, CM may serve as an ideal adjunct intervention to MT to promote long-term abstinence in HIV smokers.

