3) Inclusion and Exclusion Criteria***A. Inclusion Criteria**

To be eligible participants should:

- Diagnosed with HIV (based on self-report).
- Be 18 years and older
- Have smoked ≥ 5 cigarettes/day in the past year

- Be interested in making a quit attempt in the next 30 days
- Own a smartphone (apple/android), and plan to keep it active for the next 6 months
- Able to consent
- Have no plans to move in the next 6 months
- Are not pregnant or planning to be pregnant in the following 6 months
- Have any condition that, in the opinion of the investigator, would compromise the well-being of the patient or the study or prevent the patient from meeting or performing study requirements

B. Exclusion Criteria

Participants would be excluded if they:

- Have contraindication to NRT (past month myocardial infarction, history of serious arrhythmias/or unstable angina pectoris, dermatological disorder)
- Are currently being treated for a psychiatric condition.
- Are currently being treated for smoking cessation, alcoholism, or illicit drug use
- Are adults unable to consent
- Are individuals who are not yet adults
- Are pregnant women
- Are prisoners

4) Study Design

- a. Study Type – Interventional
- b. Primary Purpose – Other
- c. Interventional Study Model – Sequential
- d. Number of Arms – 2
- e. Randomized or not – Randomized
- f. Open label or if blinded – Not blinded
- g. Number of participants – 100

5) Procedures Involved*

We will recruit participants via community and clinic flyers and among participants of another on-going survey who smoke (IRB#20180269). In Stage 1, participants will be randomized into one of two groups: 1) a group mindfulness training (MT) for smoking cessation, or 2) contingency management (CM) for smoking cessation. In Stage 2 non-

responders (those who have not quit at 1 month evaluation) will be randomized to: 1) *Switch* to sequentially receive the other intervention (i.e., CM or MI) and complete the 3-month assessment; or 2) *Continue* without further intervention and complete the 3-month assessment only.

In stage 1, both groups will do the following:

- Complete a baseline survey.
- Receive 6 weeks of Nicotine Replacement Treatment (NRT) via mail
- Receive reminder/encouragement calls or texts the day before their quit date and 2 weeks after their quit date.

Arm 1: The MT smoking cessation intervention:

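### Section 7 plans no treatment contrast for abstinence and never uses the Stage 2 randomisation, so the SMART yields no estimate of its four strategies

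*Combined protocol and SAP*

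**What the plan says.** Section 1 calls the trial a pilot SMART and gives its aim as "to identify the optimal dynamic strategy to promote biomarker-confirmed smoking abstinence". Section 2 says the investigators "propose to test the feasibility, acceptability, and potential efficacy of a mindfulness smoking cessation intervention".

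Section 5 randomises participants to MT or CM. It then takes non-responders ("those who have not quit at 1 month evaluation) will be randomized to") and assigns them either to switch to the other intervention or to continue "without further intervention and complete the 3-month assessment only". The primary outcome is biochemically confirmed 7-day point-prevalence abstinence, with timeframe "4 weeks (end of treatment), and 3 months". Section 15 sets a target of up to 100 participants, 50 in each arm.

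The analysis text is in section 7. It will "compare the differences between arms 1 and 2", where the differences concern pre/post measures, implementation, adherence, retention and how participants viewed treatment. Cessation appears in one model: "Univariate and multivariable logistic regression models will be used to explore baseline predictors of 3-month smoking cessation". The primary outcome is otherwise reached only through a conditional remark on gender: "we will consider exploring the gender effect on our main outcomes in our analysis". The rest covers attrition, incomplete data, descriptive secondary outcomes and interviews.

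**The concern.** Two first-stage options and two second-stage options for non-responders embed 2 × 2 = 4 strategies: MT then Switch, MT then Continue, CM then Switch, CM then Continue. Choosing among them is the stated objective, and the second randomisation exists to make that possible. Section 7 mentions neither stage 2, nor responder status, nor strategies, nor weighting.

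The consequences are that the primary outcome has no planned treatment estimate, the objective has no planned analysis, and participants are re-randomised for information that the plan never extracts. Leaving the choice to the analyst has its own risks. The contrast could be picked after the data are seen, and a simple unweighted tabulation of a strategy is biased, as shown below.

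**Working it through.** **Text check.** Set against the objective, section 7 contains no stated treatment contrast on abstinence and no analysis that uses the Stage 2 assignment. A model of baseline predictors has no stated treatment term, and a gender effect is not a treatment contrast. The plan has no figure of its own to reproduce: the documents give no abstinence rate, response rate, dropout, power or effect size, and the readable text gives no Stage 2 ratio.

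**Would an arm comparison of abstinence suffice?** At 1 month it would be a clean Stage 1 contrast. At 3 months it would be a valid first-stage comparison averaged over Stage 2. To see what that average can hide, let r be the 1-month response rate, pR the 3-month abstinence in responders, pS and pC the abstinence in switched and continued non-responders, and q the share allocated to Switch.

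- Strategy value = r·pR + (1−r)·pS, or the same with pC
- Arm mean = r·pR + (1−r)·[q·pS + (1−q)·pC]

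All rates below are assumptions, with q = 0.5.

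| | r | pR | pS | pC | Switch strategy | Continue strategy | Arm mean |
|---|---|---|---|---|---|---|---|
| MT | 0.20 | 0.60 | 0.25 | 0.05 | 0.12 + 0.8×0.25 = 0.32 | 0.12 + 0.8×0.05 = 0.16 | 0.24 |
| CM | 0.30 | 0.55 | 0.15 | 0.064 | 0.165 + 0.7×0.15 = 0.27 | 0.165 + 0.7×0.064 = 0.21 | 0.24 |

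The arms tie at 24% while the strategies span 16% to 32%.

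**Sensitivity of the tie (MT minus CM).**
- CM-continue rate of 0 or 15%: CM arm mean 0.2175 or 0.27, difference +2.3 or −3.0 points. The strategies still span 16% to 32%.
- q = 1/3: 0.2133 vs 0.2299, −1.7 points. q = 2/3: 0.2667 vs 0.2499, +1.7 points. The strategy values do not change.
- CM response rate of 20% or 40%: about +4.4 or −4.4 points.
- CM responder abstinence of 40% or 70%: about +4.5 or −4.5 points.
- Counter-case, pS = pC = 0.10 in both arms: arm means of 0.12 + 0.08 = 20.0% and 0.165 + 0.07 = 23.5% equal the strategy values, and nothing is hidden.

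**Why weighting is needed.** Of 50 in MT, 10 respond (6 abstinent at 3 months) and 20 switch (5 abstinent). Unweighted, participants consistent with MT-switch give 11/30 = 36.7% instead of 32%, because all responders are counted but only half of the non-responders. Weighting by 2 and 4 gives (6×2 + 5×4)/(10×2 + 20×4) = 32/100 = 32%.

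**Precision at 50 per arm, no dropout.** With 1:1 Stage 2 allocation, the variance of a strategy estimate is [r(1−r)(pR−pN)² + r·pR(1−pR) + 2(1−r)·pN(1−pN)]/50, where pN is pS or pC. This gives 0.00735 (MT-switch), 0.00345 (MT-continue), 0.00573 (CM-switch) and 0.00415 (CM-continue). Half-width of a between-arm difference = 1.96 × √(sum of the two variances):

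- Switch vs switch: 22 points
- MT-switch vs CM-continue: 21 points
- MT-continue vs CM-switch: 19 points
- Continue vs continue: 17 points

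Simulation of 40,000 trials agrees (0.224, 0.209, 0.188, 0.170). With 20% random dropout the range becomes 19 to 25 points. Pooled Switch vs Continue, with 0.8×50 + 0.7×50 = 75 non-responders, has a half-width of about 15 points. MT vs CM at 1 month: 1.96×√(0.2×0.8/50 + 0.3×0.7/50) = 17 points. The truly best strategy ranks first in about 64% of simulated trials, or about 61% with 20% dropout.

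**The case against.** The strongest counter-reading joins three places. Section 5 puts biochemical verification of smoking status inside the baseline assessment and repeats that assessment, apart from demographics, at 3 months. Section 7 compares the arms on pre/post differences in baseline measures. An arm comparison of verified smoking status could therefore be argued to be covered. That is arguable, but section 5 lists the abstinence outcome as a separate item, and section 7 does not name it in the arm comparison. Even if the reading is granted, the result is a Stage 1 contrast that estimates no strategy.

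Second, this is a pilot with a mainly descriptive feasibility analysis. That excuses wide intervals and the absence of powered tests. It does not excuse having no estimate for the outcome named as primary or for the stated objective.

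Third, the illustration was built so that the arms tie, and the sensitivity results show that the tie moves with the rates. This stands: the example shows that an arm comparison can hide strategy differences, not that it is likely to. The omission in section 7 does not depend on it.

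Fourth, the design figure could not be read in the copy reviewed and may show the Stage 2 ratio. It could supply that input but would not replace an analysis.

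**Conclusion.** The concern holds, and it should be corrected before the data are analysed. As written, section 7 leaves the primary outcome without an explicit treatment estimate, and it leaves the second randomisation and all four strategies without any analysis. This follows from the text alone. How much an arm-level comparison would conceal is unknown: under the assumed rates the strategies differ by up to 16 points behind tied arms, and the amount is zero if Switch and Continue perform alike. The defect lies in the written analysis and not in the randomisation, since the design can support the missing estimates. Under the same assumed rates, a trial of this size can estimate the strategies but cannot reliably identify the best one.

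**What to change.** State three analyses in section 7:

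1. MT versus CM on 1-month abstinence, in all randomised participants.
2. Switch versus Continue on 3-month abstinence, among re-randomised non-responders.
3. 3-month abstinence for each of the four embedded strategies, with 95% confidence intervals. Responders count in both strategies of their arm, and non-responders are weighted by the inverse of their Stage 2 allocation probability (overall weights 2 and 4 if both stages are 1:1). Weighted proportions or a weighted-and-replicated logistic GEE with robust standard errors would both serve. Adjustment for baseline nicotine dependence is optional.

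State the Stage 2 allocation ratio in the text. State also how participants with no 1-month result are classed in (2) and (3), because they may never have been re-randomised. Restate the objective as estimating the four strategies with confidence intervals.

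The cost is wording and modest programming. The 1-month status, Stage 2 assignment and 3-month abstinence are already part of the trial. The price is a less ambitious objective and openly wide intervals.
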